Gradual withdrawal (2 cm every several days) of surgically placed drains in patients who are clinically stable and tolerate a diet is generally adopted to hasten closure of POPF.⁸ In brief, drain withdrawal is initiated after postoperative days 5 to 7 and continued at outpatient visits until output is less than 10 mL per day, and then the drain is removed. For high-output fistulas (> 150–200 mL of amylase-rich fluid per day), patients are initially managed with fasting and enteral or parenteral nutrition. If fistula output decreases substantially with these measures and the patient remains clinically well, drain withdrawal is initiated and oral intake is slowly restarted. If fistula output fails to decrease with these measures, drains are initially left in place to control the fistula. If the patient remains well despite high fistula output, drains are slowly withdrawn in an attempt to decrease the output

and close the fistula. If patient develops fever, abdominal pain, or an inability to tolerate oral intake, drains are not withdrawn and an abdominal computed tomographic (CT) scan is arranged. If any drainable fluid collection is identified, the patient is treated with broad-spectrum antibiotics and undergoes interventional radiology–guided drainage, which is kept in place and flushed daily. When the output decrease to less than 10 mL per day, the drains are removed.

However, the current standard practice of gradual drain withdrawal is time consuming. Although clinically stable can be discharged with the drain, the drainage tube often remains in place for a prolonged period, with patient discomfort and increased medical cost. In our pilot study, 32.5% (37/114) of POPF patients required drainage for longer than 21 days. Besides, there is also considerable risk of recurrent fluid collection along the drain tube tract after drain removal.¹¹ Measures that can accelerate drain removal and reduce the risk of recurrence may reduce POPF-related morbidity and reduce hospital costs and length of stay.

1.1 Investigational Treatment

Our experience has shown that trans-drain occlusion of the drain tract achieves fistula closure, enabling immediate removal of the drain. Trans-catheter occlusion requires the fluid collection to become walled-off, which usually takes 3 weeks. As the walled-off fluid collection can drain either via the percutaneous drain or via the pancreatic duct into the jejunum, occluding the point of entry of the drain tube into the fluid collection by gelfoam stops further fluid flowing through the drain tube. After occlusion, the secreted pancreatic juice can only drain through the pancreatic cut into the jejunum, and therefore the drain can

be removed right after embolization without recurrence of fluid collection along the tract of the drain.

1.2 Preclinical Data

In a pilot study, 20 patients underwent trans-catheter occlusion for POPFs that persisted for more than 3 weeks after placement of drainage tubes. No subjective symptoms or abnormalities in blood tests were noted in 17 patients after the procedure. Three patients had abdominal pain without signs of infection, and the pain spontaneously subsided after conservative treatment. POPF healed immediately after occlusion in all of the 20 patients without recurrence during follow-up.

1.3 Risk/Benefits

In the aforementioned pilot study, occlusion achieved rapid closure of POPF in all the patients. Pain developed in 3 of 14 patients (21.4%) after occlusion that resolved uneventfully after conservative treatment. No other adverse effects were noted. These preliminary results suggest that trans-catheter occlusion is effective in achieving rapid POPF closure with minimal risk.

1.4 Trial Conduct

This study will be conducted in compliance with the protocol approved by the Institutional Review Board, and according to Good Clinical Practice standards. No deviation from the protocol will be implemented without the prior review and approval of the IRB except where it may be necessary to eliminate an immediate hazard to a research subject. In such case, the deviation will be reported to the IRB as soon as possible.

1.5 Population

Patients 18 years of age or older who undergo pancreatic resection and subsequently develop POPF (i.e. drain output of any measurable volume of fluid on and after postoperative day 3 with amylase content > 3 times ULN) that persists for longer than 3 weeks are target population of the trial.

During surgery, 7mm-calibered drains are placed before closing the wound; the type, number of drain tubes placed and the location of placement are at the discretion of the operating surgeon. The number and amylase concentration of the drainage fluid is measured on the 3rd, 5th, and 7th postoperative day, and when drainage color changes. POPF is defined as a drain output of any measurable volume of fluid on and after postoperative day 3 with an amylase content > 3 times the upper limit of normal serum level.⁹ After the diagnosis of POPFs, the route of nutrition is (oral, enteral, or parenteral) is at the discretion of the doctor caring the patients. Patients are assessed daily for fistula output and fistula- or treatment-related complications. If fever occurs, broad-spectrum antibiotics are administered and abdominal CT is performed. Additional interventional radiology-guided catheter drainage is performed for any drainable fluid collections identified by CT. If output of a drain tube is below 10 ml during 48 hours, the drain tube is removed. If a drain tube (rarely more than 1) still cannot be removed on day 21 from the onset of POPF, the patient is diagnosed to have a POPF that persists for 3 weeks and further evaluated for eligibility and enrollment.

This is a multicenter, investigator initiated, prospective, superiority, parallel-group, randomized, double-blinded trial to compare trans-drain occlusion followed by gradual withdrawal of drain and gradual withdrawal of drain alone.

3.1 Primary Study Endpoints/Secondary Endpoints

Efficacy end points:

- The primary efficacy end point is the days from the randomly allocated treatment to fistula closure. The date of fistula closure is defined as the date on which the drain is removed after an output of ≤ 10 mL during 48 hours, without recurrence of POPF within the next 3 months.
- Secondary efficacy end points:
 - 30-day fistula closure rate: the proportion of patients in whom the drain can be removed by 30 days after occurrence of POPF, without recurrence of POPF within the next 3 months.
 - Rate of persistent or recurrent POPF after initial drain removal: the proportion of patients with fluid collection^a on follow-up CT, which is to be performed at 3 months after removal of drain or when recurrence of POPF is suspected clinically.
 - Length of hospital stay and hospital costs after the assigned treatment.
 - Rate of fistula-related complications: the proportion of patients who develop fever/infection^b, ileus^c, postpancreatectomy hemorrhage (PPH)^d from undergoing the assigned treatment to end of follow-up.

Safety end points:

- Fever/infection* or pain** that develops within 48 hours after the allocated treatment, or any adverse events judged to be related to the treatment.

[figure not shown]
*Fever/infection: body temperature $\geq 38.5^{\circ}\text{C}$, leukocytosis (WBC count $>12,000$ /uL) or leukopenia (WBC count $<4,000$ /uL)

**Pain: new-onset or worsening of pre-existing pain (≥ 1 point increase in VAS).

3.2 Study Design/Type

This trial is a prospective, superiority, parallel-group, randomized, double-blinded trial.

CONSORT 2010 Flow Diagram

3.3 Randomization

Patients fulfilling the inclusion and exclusion criteria will be randomly assigned in a 2:1 ratio to receive embolization or standard care. Block randomization is performed, stratified according to center. For each participating center, a randomization list is produced randomly with block size of 3. The Research Electronic Data Capture (REDCap) software program is used to generate randomization numbers.

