3.4 Maintenance

The randomization procedure will be conducted and maintained by Clinical Trial Statistical Center, National Taiwan University Hospital.

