3.5 Trial Treatment

In patients randomized to receive standard care, only fistulography is performed to assess the condition of the fistula; occlusion is not performed. However, after fistulography, the drainage tube will be pulled outward for 2 cm in length and then fixed at skin again. Thereafter if patient remains asymptomatic, the drainage tube will be gradually withdrawn by 2 cm in length each day. The drainage tube will be removed when 48 hours drainage amount is less than 10 cc.

In patients randomized to undergo occlusion, the patient receives fistulography to assess the condition of the fistula, and then occlusion is performed using the following methods:

- In patients with a 7mm-calibered CW(closed wound) drain (perforated flat drain or round channel drain):

1. Use a Kelly or Mosquito forceps to clamp the tube of CWV drain.

[figure not shown]
2. Then an 18G puncture needle is inserted into the tube and remove the inner needle.

The small amount of diluted contrast medium can be slowly injected into the CWV tube. The tube and the route can be more clearly identified (fistulography).

3. A 0.035-inch guidewire can be inserted via the 18G puncture needle.

4. Remove the CW drain under the fluoroscopy. There may be some resistance initially when removing the CW drain. The proximal part of the removed CW drain is cut at 4 cm proximal to the previous skin fixation site (as shown in the following figure) and preserved in sterility for reinsertion.

5. A 40cm, 5Fr KMP catheter (Cook company) is inserted via the guidewire, and then the guidewire is removed.

6. Rinse the catheter hub and KMP catheter with 3ml 5% glucose water (Dextrose). Then the glue (33%, 1:2, 0.5ml of NBCA + 1ml Lipiodol) is slowly injected into the KMP catheter. Withdraw the catheter and continuously inject the glue until 5cm-long catheter remained inside the tract. The guidewire is inserted back through the catheter.

7. The planned reinserted portion of the original drain tube is inserted back into the drain tract via the guidewire. The guidewire is removed and the drain tube is fixed to the skin at previous fixation site.

8. Thereafter if patient remains asymptomatic, the drainage tube will be gradually withdrawn by 2 cm in length each day. The drainage tube will be removed when 48 hours drainage amount is less than 10 cc.

- In patients with a pigtail drainage of the post-operative fluid collection:

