3.6 Duration

If drain(s) cannot be removed after 21 days from the occurrence of POPF, the patient is enrolled and randomized if he or she fulfils the eligibility criteria, and then receives the assigned treatment. After undergoing the assigned treatment, patients are assessed daily for drain output and any complications. Drains are removed when the drainage amount is below 10 ml during 48 hours, and patients are discharged if they tolerate oral intake well and remain afebrile for 2 days after removal of all drains. After discharge, in-office visits were scheduled at week 1, 2, 4, 8, and 12. A follow-up CT is performed when there is clinical suspicion of POPF recurrence, or at 3 months after removal of the drain, whichever comes first. Therefore, the expected duration of subject participation is between 3 to 4 months.

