4.2 Exclusion Criteria

- Patients are excluded if they are younger than 20 years of age, have active infection that is not adequately controlled [defined as body temperature $\geq 38.5^{\circ}\text{C}$ and/or leukocytosis (WBC count $>12,000$ /uL) or leukopenia (WBC count $<4,000$ /uL)], have current or history of severe heart, lung, kidney, or liver failure, have a Karnofsky Performance Score of <60 , are pregnant or lactating, or have received somatostatin or its analogue during the index admission, or decline to participate.

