7.2 Sample Size Estimation

With 2:1 randomization, it is estimated that 51 patients, 34 for the occlusion group and 17 for the standard care group, are needed to have 80% power to detect a hazard ratio for removal of drain of 2.5, on the basis of a log-rank test with a two-sided significance level of 5%. Assuming a 10% dropout rate, the planned number of patients to be enrolled is 57, 38 for the occlusion group and 19 for the standard care group. All randomized subjects are analyzed according to intention-to-treat.

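### One printed block size of 3, at 2:1 within each centre, makes up to 44% of allocations on average certain to anyone who knows that centre's earlier allocations; randomly mixed blocks of 3 and 6 would cut this cheaply

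*Combined protocol and SAP*

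**What the plan says.** Section 3.3 has patients "randomly assigned in a 2:1 ratio to receive embolization or standard care". The only stratification factor is the centre ("Block randomization is performed, stratified according to center"), and the block size is a single printed value: "For each participating center, a randomization list is produced randomly with block size of 3". No varying or undisclosed size is mentioned.

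On custody, section 3.4 says "The randomization procedure will be conducted and maintained by Clinical Trial Statistical Center". No section describes how the next allocation is kept from the person enrolling.

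Section 3 and section 3.2 call the trial double-blinded without saying who is blinded. Under section 3.5 the two procedures differ physically. In the control arm "only fistulography is performed to assess the condition of the fistula; occlusion is not performed", whereas in the occlusion arm the drain is taken out, glue is injected and part of the drain is put back.

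Entry is described in section 3.6: "If drain(s) cannot be removed after 21 days from the occurrence of POPF, the patient is enrolled and randomized", subject to eligibility. Section 7.2 gives the size: "the planned number of patients to be enrolled is 57, 38 for the occlusion group and 19 for the standard care group". The number and sizes of centres are not given.

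**The concern.** Three is the smallest block that can hold a 2:1 ratio. With a fixed and known size, a centre's past allocations reveal part of its future ones: once the control in a block has been used, the rest must be occlusion, and after two occlusions the next must be control. Holding the list centrally does not prevent this, because the deduction uses past cases and not the list. Whoever performs the procedure learns the arm, so the history can be known at the site.

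What is at stake is selection at entry. A person who both knows the history and influences enrolment could hold back or encourage a patient when the next arm is foreseeable. The comparator has only 19 planned patients, so a few selectively entered controls would not be negligible.

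**Working it through.** **Inputs.** Ratio 2:1, block size 3 and one list per centre (section 3.3); 57 planned patients (section 7.2). The number and sizes of centres are assumptions, shown as a range.

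**The plan's total.** 51 / (1 - 0.10) = 56.7, so 57; 34 / 0.9 = 37.8, so 38; 17 / 0.9 = 18.9, so 19. These reproduce.

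**One block.** With T for occlusion and C for control, the equally likely orders are TTC, TCT and CTT. An allocation is certain when all remaining places in the block belong to one arm.

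- Certain places: 1, 1 and 2, mean 4/3 of 3 = 44.4%.
- Of these, 1 per block is occlusion and 1/3 is control, so 75% are occlusion.
- Best guess: 2/3 + 2/3 + 1 = 7/3 correct of 3 = 77.8%. Always guessing occlusion gives 66.7%.

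**A centre of n patients.** Expected certain allocations = (4/3) × floor(n/3), plus 1/3 if n leaves remainder 2. That extra 1/3 is always occlusion, so incomplete blocks lower the total and raise the occlusion share above 75%.

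**Lowest and highest share over all splits of 57:**

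| Centres | Lowest | Highest |
|---|---|---|
| 1 | 44.4% | 44.4% |
| 5 | 39.8% | 44.4% |
| 8 | 36.8% | 44.4% |
| 12 | 32.7% | 44.4% |
| 20 | 25.1% | 42.7% |

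For example, eleven centres of 5 plus one of 2 give 11 × 5/3 + 1/3 = 18.67 of 57 = 32.7%.

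These are expectations. A realised list of 19 complete blocks has 19 + Binomial(19, 1/3) certain places: possible range 19 to 38 (33-67%), central 95% range 22 to 29 (39-51%).

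**Comparison with random blocks of 3 and 6.** The two sizes are equally likely. The observer knows this new rule and the centre's history and updates by Bayes' theorem. There were 6,000 simulated trials per split, with all 57 patients allocated under one rule. Repeat runs moved the certain count by no more than about 0.1 patient.

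| Assumed split of 57 | Certain, blocks of 3 | of which control | Best guess correct | Certain, 3/6 | of which control | Best guess correct |
|---|---|---|---|---|---|---|
| One list of 57 | 25.3 (44.4%) | 6.3 | 77.8% | 5.67 (9.9%) | 1.22 | 75.4% |
| 3 × 19 | 24.0 (42.1%) | 6.0 | 77.2% | 5.20 (9.1%) | 1.04 | 74.8% |
| 20/13/10/7/4/3 | 23.0 (40.4%) | 5.7 | 76.6% | 4.55 (8.0%) | 0.86 | 74.1% |
| 7 × 8 + 1 | 21.0 (36.8%) | 4.7 | 74.9% | 4.20 (7.4%) | 0.80 | 73.0% |

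Certain controls are thus 8-11% of patients now. Best-guess accuracy falls by 1.9-2.5 points, or 1.1-1.4 correct guesses in 57, so the gain is mainly in certain allocations.

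Enlarging a fixed block is not equivalent: a fixed, known 6 (4:2) with complete blocks still leaves (4/3 + 2/5) / 6 = 28.9% certain.

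**The case against.** The strongest reply is that the harm needs someone whom the documents do not describe: a person who knows a centre's whole sequence and also controls entry. Section 3.5 shows that the operator sees the arm. It does not show that the operator recruits, or that one operator sees every case. This stands, and it limits what can be concluded.

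Discretion at entry is also narrow. It is triggered by a drain still in place at day 21 (sections 1.5 and 3.6), and the infection exclusion in section 4.2 has numeric limits. Some judgement remains: "have current or history of severe heart, lung, kidney, or liver failure" carries no threshold for severity, and how the trial is offered can vary. The route is narrowed, not closed.

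A small block protects balance within small centres, which is a legitimate reason to choose it. The cost of relaxing it is modest and is given with the fix.

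Three stronger readings are tempting, and the documents support none of them:

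- That about 37% is a floor. It holds only for 8 or fewer centres; section 3 says only that there are several.
- That 44% measures usable information. At least three quarters of the certain allocations are to the arm one would guess anyway.
- That concealment has failed or the result is biased. Nothing shows that anyone had or used the information, and the size of any bias cannot be derived.

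**Conclusion.** The point holds as an avoidable weakness in allocation concealment. The expected share of certain allocations is up to 44%, at least about 37% with 8 or fewer centres, and as low as 25% with 20. In the four splits examined, all with 8 or fewer centres, certain controls are about 5 to 6 of 57. The block arithmetic is exact. The lower limits rest on an assumed number of centres and on 57 patients enrolled, and every figure supposes an observer who knows the centre's history. It warrants a cheap improvement and does not call the design into question.

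**What to change.** For allocations still to be made, have the statistical centre generate each centre's list with block sizes of 3 and 6 chosen at random. Start the new list in a centre once its current block is complete. Record the sizes in a document held only by the statistical centre, and delete the block size from the protocol text that sites hold. The ratio, stratification, sample size and analysis are unchanged. The gains tabulated above do not rely on the rule staying secret, because the simulated observer knows it. They do assume that all 57 patients are allocated under it, so a switch partway gains less.

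The cost is a new list and one wording change, submitted to the IRB as an amendment under section 10. The statistical downside is slightly looser balance in small centres. For a centre allocated wholly under the new rule, the chance of no control is 0.5 × 4/20 = 10% with 3 patients and 0.5 × 1/15 = 3.3% with 4, against 0% now. The 95% range for total controls barely moves: 17-21 under both rules in the six-centre split, from 16-21 to 16-22 in the eight-centre split, and from exactly 19 to 18-20 with a single list of 57.

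The documents do not show enrolment status. If no allocations remain, the list change does not apply.

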3.4 Maintenance

The randomization procedure will be conducted and maintained by Clinical Trial Statistical Center, National Taiwan University Hospital.

3.5 Trial Treatment

In patients randomized to receive standard care, only fistulography is performed to assess the condition of the fistula; occlusion is not performed. However, after fistulography, the drainage tube will be pulled outward for 2 cm in length and then fixed at skin again. Thereafter if patient remains asymptomatic, the drainage tube will be gradually withdrawn by 2 cm in length each day. The drainage tube will be removed when 48 hours drainage amount is less than 10 cc.

In patients randomized to undergo occlusion, the patient receives fistulography to assess the condition of the fistula, and then occlusion is performed using the following methods:

- In patients with a 7mm-calibered CW(closed wound) drain (perforated flat drain or round channel drain):

1. Use a Kelly or Mosquito forceps to clamp the tube of CWV drain.

[figure not shown]
2. Then an 18G puncture needle is inserted into the tube and remove the inner needle.

The small amount of diluted contrast medium can be slowly injected into the CWV tube. The tube and the route can be more clearly identified (fistulography).

3. A 0.035-inch guidewire can be inserted via the 18G puncture needle.

4. Remove the CW drain under the fluoroscopy. There may be some resistance initially when removing the CW drain. The proximal part of the removed CW drain is cut at 4 cm proximal to the previous skin fixation site (as shown in the following figure) and preserved in sterility for reinsertion.

5. A 40cm, 5Fr KMP catheter (Cook company) is inserted via the guidewire, and then the guidewire is removed.

6. Rinse the catheter hub and KMP catheter with 3ml 5% glucose water (Dextrose). Then the glue (33%, 1:2, 0.5ml of NBCA + 1ml Lipiodol) is slowly injected into the KMP catheter. Withdraw the catheter and continuously inject the glue until 5cm-long catheter remained inside the tract. The guidewire is inserted back through the catheter.

7. The planned reinserted portion of the original drain tube is inserted back into the drain tract via the guidewire. The guidewire is removed and the drain tube is fixed to the skin at previous fixation site.

8. Thereafter if patient remains asymptomatic, the drainage tube will be gradually withdrawn by 2 cm in length each day. The drainage tube will be removed when 48 hours drainage amount is less than 10 cc.

- In patients with a pigtail drainage of the post-operative fluid collection:
 1. The small amount of diluted contrast medium can be slowly injected into the pigtail to localize the tube location.
 2. A 0.035-inch guidewire is inserted via the pigtail hub.
 3. Remove the pigtail under the fluoroscopy. The proximal part of the removed CW drain is cut at 4 cm proximal to the previous skin fixation site (as shown in the following figure) and preserved in sterility for reinsertion.
 4. A 40cm 5Fr KMP catheter (Cook company) is inserted via the guidewire, and then the guidewire is removed.

5. Rinse the catheter hub and KMP catheter with 3ml 5% glucose water (Dextrose). Then the glue (33%, 1:2, 0.5ml of NBCA + 1ml Lipiodol) is slowly injected into the KMP catheter. Withdraw the catheter and continuously inject the glue. The guidewire is inserted back through the catheter and the planned reinserted portion of the original pigtail drainage tube is inserted back into the drain tract via the guidewire. The guidewire is removed and the pigtail drain tube is fixed to the skin at previous fixation site

6. Thereafter if patient remains asymptomatic, the drainage tube will be gradually withdrawn by 2 cm in length each day. The drainage tube will be removed when 48 hours drainage amount is less than 10 cc.

